9.2 Appendix B Technical details missing data imputation model for UACR

The evaluation of the secondary efficacy endpoint UACR is the ratio of change from baseline to Month 4 in UACR. In case of a missing value at Month 4 (on or off treatment) the subject will be excluded from this analysis. This strategy leads to unbiased estimates of the treatment effect only if the missing data are “missing completely at random” (MCAR), i.e. the missingness is independent of both observed and unobserved outcomes. Although this condition might hold approximately, they are unlikely to hold exactly. In accordance with the EMA “Guideline on missing data in confirmatory clinical trials” other ways of handling missing data will be investigated.

Missing not at random (MNAR) means that missingness depends both on observed and unobserved outcomes. This requires an explicit model for the patient’s statistical behavior after drop-out. A fixed increase above the group average for patients dropping out can be assumed, where the pattern and size of the increase is varied across several sensitivity analyses. This is sometimes called the delta method of sensitivity analysis in a pattern mixture framework (see reference 8, Chapter 6).

The following scenarios of no penalty and fixed penalties after drop-out will be investigated, where different values are assigned to the treatment groups:

Penalties after drop-out (ratio baseline : Month 4), based on an expected ratio from baseline to Month 4 on finerenone of 0.70.

- Placebo 0 / finerenone 0
- Placebo 0 / finerenone +0.15
- Placebo 0 / finerenone +0.30
- Placebo +0.15 / finerenone +0.15
- Placebo +0.15 / finerenone +0.30
- Placebo +0.30 / finerenone +0.30
- Tipping point analysis: Placebo 0 / finerenone +X, X is the value where the p-value of the difference between placebo and finerenone becomes 0.05 (two-sided).

To properly account for the incompleteness of the data, multiple imputation will be used to draw sets of completed data that will then be modified according to the scenarios given above. Multiple imputation will be done using SAS PROC MI using the following generic code, where stratification group are coded as dummy variables using the first factor in each stratification group as the respective reference groups:

```
PROC MI data=<dataset> seed=<study number> nimpute=50
out=<output dataset>;
  BY trtgrp;
  MCMC niter=500 nbiter=500;
  VAR logUACRbase logUACRmonth4 <stratumn>
RUN;
```

After modifying the completed data sets according to the scenarios, the ANCOVA of the main analysis will be performed at Month 4 for each completed data set. The results are then combined using SAS PROC MIANALYZE.

For each scenario, the ratio of treatment difference at Month 4 from baseline will be given with a 95%-confidence interval and a p-value.

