10.3.3.3 Secondary efficacy variables: primary analysis

The primary analysis of the secondary efficacy variables will be analyzed in FAS.

If the null hypothesis of the primary analysis is rejected, the secondary efficacy variables will be tested hierarchically in the order as they are listed in Section 9.4.2, while keeping the two-sided significance level of 5.0%. Otherwise, the testing of the secondary efficacy variables will be performed in an explorative manner only.

The primary analysis of the secondary time-to-event endpoints will be analyzed analogously to the primary analysis of the primary composite endpoint.

An ANCOVA model will be fitted to the logarithmized ratios of UACR at Month 4 to UACR at baseline including the factors treatment group, the stratification factors (type of albuminuria, region, eGFR category, history of CVD) and the logarithmized baseline UACR as covariate. Corresponding two-sided 95% confidence intervals will be computed. This is consistent with the primary analysis of the Phase II Study 16243.

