4.7 Testing procedure and multiplicity adjustment

If the decision will be to stop the study early for success (see section 4.4 for a description of the stopping rules), the final primary analyses, both for the primary and secondary efficacy endpoints, will be performed at a two-sided significance level of 0.270%. Only if both the primary and the key secondary efficacy endpoint achieve this significance level, the corresponding null hypotheses can be rejected and the remaining secondary endpoints will also be tested at a two-sided level of 0.270% according to the following hierarchy:

- Time to all-cause hospitalization
- Time to all-cause mortality
- Change in UACR from baseline to Month 4
- Time to first occurrence of the following renal composite endpoint: onset of kidney failure, a sustained decrease in eGFR of $\geq 57\%$ from baseline over at least 4 weeks or renal death

If the decision will be not to stop the study early for success, the final primary analyses will be performed as follows: A group sequential design with a single interim analysis when 2/3 of the information is available with a stopping rule of two-sided $p < 0.00270$ requires a small adjustment to the final analysis that is slightly lower than $p = 0.05$ to maintain the overall significance level at 5%. A hierarchical testing procedure will be used for the primary and secondary efficacy variables in the order mentioned below with each variable being tested at the adjusted two-sided significance level of 0.04967388, which applies for an information fraction of 2/3.

- Primary CV composite endpoint
- Key renal composite endpoint
- Remaining secondary efficacy endpoints as in the order mentioned above for a stop at the interim analysis

If the testing strategy stops at one point due to a non-significant result, the testing of the remaining secondary efficacy variables will be performed in an explorative manner only.

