- Estimate the hazard at time of loss to follow-up, using a Weibull survival model fitted to the population of subjects who prematurely discontinued study treatment and adjusted for treatment group and stratification factors.
- Inflate the hazard only in the finerenone group by a known factor; assumes non-informative censoring in the control group.
- Impute events to the end of the study 1000 times, calculate the hazard ratios with the stratified Cox model specified in section 6.2.1.1 and combine them using standard multiple imputation combining rules.
- Increase the inflation factor until upper limit of two-sided 95.032612% (or 99.73% at the interim analysis) confidence interval for the hazard ratio crosses 1.0; this will be the “tipping point”.

The tipping point will show how much higher the event risk after drop-out would need to be in the finerenone group so that statistical significance is lost. Since there is no particular reason to assume that the event rate should be higher, a large tipping point will indicate robustness of the study results. Technical details of the model are provided in section 9.1.

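### SAP 9.2 sets the UACR tipping point at p = 0.05, which is not the level at which SAP 4.7 tests UACR; this matters only after an early stop in which the testing hierarchy reaches UACR

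*SAP*

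**What the plan says.** SAP 4.7 lists "Change in UACR from baseline to Month 4" third among the four secondary endpoints that follow the key renal composite. There are two branches.

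- **Early stop for success.** Once the primary and key renal endpoints have passed, "the remaining secondary endpoints will also be tested at a two-sided level of 0.270% according to the following hierarchy".
- **No early stop.** The primary and secondary endpoints are tested in sequence, "with each variable being tested at the adjusted two-sided significance level of 0.04967388".

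In the second branch, a non-significant result makes all later endpoints exploratory.

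For the primary endpoint, SAP 6.2.1.2 ties the tipping point to these levels: "Increase the inflation factor until upper limit of two-sided 95.032612% (or 99.73% at the interim analysis) confidence interval for the hazard ratio crosses 1.0". It presents the tipping point as the excess risk after drop-out at which statistical significance disappears. SAP 9.1 uses the same 95.032612% interval for the final analysis.

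For UACR, SAP 9.2 gives a single threshold for all circumstances: "X is the value where the p-value of the difference between placebo and finerenone becomes 0.05 (two-sided". It also asks for a 95% confidence interval and a p-value for every scenario. No section exempts UACR from the levels in 4.7.

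**The concern.** A tipping point answers one question: how bad must the unobserved outcomes be before the declared significance is lost? It answers that only if the search stops at the level at which significance was declared. The 0.05 in SAP 9.2 is not a level at which 4.7 tests UACR in either branch.

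After an early stop the gap is wide, 0.05 against 0.00270. The search passes the point at which the confirmatory result fails and reports a larger penalty than the result can bear. A UACR result with p between 0.0027 and 0.05 would receive a positive tipping penalty although the 0.270% test had already failed. At stake is how the missing-data robustness of one secondary endpoint is described.

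**Working it through.** **1. The SAP's adjusted level.** Inputs from SAP 4.4 and 4.7: one interim at information fraction 2/3, boundary |z| > 3 (two-sided p = 0.0027), and "to maintain the overall significance level at 5" percent. With interim and final statistics bivariate normal with correlation √(2/3), solve for the final two-sided level that gives 0.05 overall. The result is 0.049674, which agrees with the SAP's 0.04967388. Also 1 − 0.04967388 = 0.95032612, the confidence level used in 6.2.1.2.

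**2. Critical values.**

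| Threshold | Two-sided p | Critical z |
|---|---|---|
| SAP 9.2, always | 0.05 | 1.960 |
| SAP 4.7, no early stop | 0.04967388 | 1.963 |
| SAP 4.7, early stop | 0.00270 | 3.000 |

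The direction follows without further assumptions: after an early stop, X at z = 1.960 always exceeds X at z = 3.000.

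**3. Size.** From the documents: about 7400 patients randomized 1:1, so n = 3700 per arm, and an expected finerenone ratio of 0.70. Assumed, because the documents do not give them: placebo ratio 1.0, residual SD of log UACR 0.6 to 1.0, and a fraction m = 5 to 10% missing at Month 4. The imputed data are treated as complete.

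Let r be the finerenone ratio and d the log-scale penalty for missing finerenone patients. The tipping value solves

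−ln(r) − m·d = z × SE(d), with SE(d) = √{[SD² + m(1−m)d²]/n + SD²/n}.

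On the SAP's ratio scale, X = r(e^d − 1).

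*Expected effect, r = 0.70, SD 0.8, m = 10%.* The effect is −ln 0.70 = 0.3567 and the unpenalized SE is 0.8 × √(2/3700) = 0.0186, so z = 19.2.

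- At 0.05: d = 3.095. Check: 0.3567 − 0.3095 = 0.0472; SE(d) = 0.0241; 1.960 × 0.0241 = 0.0472. X = 14.76.
- At 0.04967388: X = 14.75.
- At 0.0027: d = 2.866, X = 11.60.
- Log-scale overstatement after an early stop: 3.095/2.866 = 1.08.

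Over the whole assumed range at r = 0.70, the log-scale overstatement is 1.07 to 1.11. Without an early stop, X changes by less than 0.2%.

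*Weaker effect, r = 0.90, SD 0.8, m = 10%.* The effect is 0.1054 and z = 5.7.

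- At 0.05: d = 0.683, X = 0.90 × (e^0.683 − 1) = +0.88.
- At 0.0027: d = 0.491, X = +0.57.

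X is 0.88/0.57 ≈ 1.5 times too large, and d is 0.683/0.491 = 1.39 times too large.

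*Very weak effect, r = 0.95, SD 0.8, m = 10%.* Here z = 2.8. The result already fails at 0.0027 without any penalty, yet SAP 9.2 would report X = +0.15.

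**The case against.** **The condition is narrow.** An early stop is not enough. Four endpoints (primary, key renal, all-cause hospitalization, all-cause mortality) must each pass at 0.270% before UACR is tested confirmatorily. If any fails, UACR has no confirmatory significance to lose. This stands and limits the point.

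**The conclusion is unchanged at the expected effect.** A reader who works on the ratio scale might take the overstatement at r = 0.70 to be 1.23 to 1.78 times and call it large. That figure compares penalties that are all implausible. The smallest X at p = 0.0027 in the assumed range is 10.3, against a largest fixed penalty of +0.30 in SAP 9.2, and exponentiation enlarges the contrast. No plausible penalty overturns the result at either threshold.

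**The information is largely there already.** SAP 9.2 reports a p-value for each fixed scenario, including no penalty, and labels X as the p = 0.05 point. In the r = 0.95 example the no-penalty p-value would itself exceed 0.0027. The 0.05 threshold also agrees with the 95% intervals reported for UACR. This reduces the risk of misreading, but X still does not describe loss of the declared significance, which is the purpose stated in 6.2.1.2.

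**Stronger readings that the documents do not support.** A reader might infer that UACR has several conflicting test levels, since protocol 10.3.3.3 has the secondary endpoints "tested hierarchically in the order as they are listed in Section 9.4.2, while keeping the two-sided significance level of 5.0" percent. But protocol 10.5 already gives 0.270% after an early stop, for primary and secondary endpoints, and 4.968% otherwise; and SAP 9.2 sets a sensitivity threshold, not a test level. A reader might also infer that the confirmatory decision or its error rate is compromised. It is not: SAP 4.7 alone governs the decision, and SAP 6.2.2.2 classes these as sensitivity analyses.

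**Conclusion.** The point holds as a small internal inconsistency. The threshold in SAP 9.2 is not the level at which UACR is tested, and the SAP's own primary tipping-point analysis shows the intended approach.

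The consequence is confined to an early stop in which the four preceding endpoints have passed at 0.270%. There the direction is certain: X is too large. The size rests on the assumed SDs and missing fractions. It is about 7 to 11% on the log scale at the expected ratio of 0.70, without effect on the qualitative conclusion, and it becomes material only for a weak UACR effect, such as a ratio of 0.90. If the study runs to its final analysis the difference is negligible.

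**What to change.** Change the SAP only.

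1. In 9.2, let the tipping value X be the one at which the p-value *becomes the two-sided level at which UACR is tested under section 4.7 (0.04967388, or 0.00270 if the study stops early for success)*.
2. In 9.2, report the tipping-point scenario with the matching confidence interval, 95.032612% or 99.73%. Otherwise a scenario tipped at p = 0.0027 would appear beside a 95% interval that still excludes no effect.

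No protocol change is needed, because protocol 10.5 already states the adjusted levels.

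The cost is a short SAP edit, one program constant and one interval level. After an early stop the reported tipping point becomes slightly less favourable at the expected effect; otherwise the output is practically unchanged.

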9.3 Appendix C Region grouping

The following regions have been defined as used for stratification:

- North America,
- Latin America,
- Europe,
- Asia,
- Others

Region grouping is based on the location of a country to that continent, which in most cases is unambiguous. These rules have been used for the following countries:

- Israel and Saudi Arabia are geographically located in Asia, and have been allocated to that region.
- Turkey and Russia are located in both Europe and Asia; they have been allocated to region Europe.
- Mexico is allocated to region Latin America.
- Puerto Rico is in the Caribbean and an unincorporated US territory; it is therefore linked to the US and included in North America.
- Others includes countries in Africa and Australasia: South Africa, Australia and New Zealand.

The IxRS stratification scheme has Italy, China and Japan as their own individual stratification groups, due to the ixehol substudy (Italy) and regulatory requirements to demonstrate consistency with the main study (China, Japan). For region groupings, Italy will be included with Europe, China and Japan with Asia.
